#### 4.2.3.6 Planned Exploratory Biomarker Research

Mechanistic markers of anti-LAG-3/anti-PD-1 combination activity have been observed after administration of the surrogate monoclonal antibody (mAb) 28G10 in mouse syngeneic tumor models, including induction of gene expression changes of various immune mediators (eg, interferon gamma [IFN- $\gamma$ ], perforin, and granzymes). These changes in candidate pathway biomarkers are predominantly seen within the tumor, though some transient changes in gene expression in peripheral blood were observed. Immunophenotyping by immunohistochemistry (IHC) and gene expression profiling of tumor biopsies, and by whole blood flow cytometry will be performed to explore changes in lymphocyte populations. These include the expression of LAG-3, MHC Class II, and PD-L1 by IHC as well as levels of IFN- $\gamma$ -pathway genes, effector T-cell response genes, T-cell immunomodulatory receptors (IMRs), and other related markers of immune response. Additional candidate biomarkers including positivity for human papillomavirus (HPV), Epstein-Barr virus (EBV), human epidermal growth factor receptor 2 (HER2/neu), and microsatellite instability (MSI) will also be assessed by appropriate tests.

Subjects will be required to provide an archival tumor tissue sample and/or a fresh biopsy of tumor before treatment for these biomarker analyses. Subjects will also be asked to agree to a biopsy of tumor after initiation of study treatment and to provide the acquired tissue for these biomarker analyses.

Immune modulatory agents may alter populations of circulating immune cells in blood. To assess the effect of MK-4280 on these cell populations, peripheral blood samples will be obtained at designated times before and after study treatment. Changes in immune cell populations will be evaluated by comparing changes in T-cell repertoire and expression of immune function genes or proteins from baseline to after treatment.

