- iii. Have documented PD within 24 weeks of the last dose of anti-PD-1/PD-L1 mAb. Patients who were re-treated with anti-PD-1/PD-L1 mAb and patients who were on maintenance with anti-PD-1/PD-L1 mAb will be allowed to enter the trial as long as

there is documented PD within 24 weeks of the last treatment date (with anti-PD-1/PD-L1 mAb).

e. **Cohort E** - Adenocarcinoma of the stomach and/or gastric-esophageal junction (GEJ) that is considered inoperable and that has received, and progressed on, at least 1 prior chemotherapy regimen or HER2/neu-targeted approved therapy (if HER2/neu-positive). In both cases, subjects must not have been treated with prior anti-PD-1/PD-L1 therapy.

*Note – Subjects with known MSI high or MMR deficient gastric cancer or CRC (as determined by either PCR or IHC) are excluded from participating in this study. MSI high is defined as at least 2 allelic shifts occurring among the 5 analyzed microsatellite markers as detected by PCR. MMR deficient is defined as loss of expression of at least 1 of 4 proteins (MLH1, MSH2, MSH6, and/or PMS2) by IHC. If a subject's MSI/MMR status is unknown, testing is not required to determine eligibility.*

*Note – Subjects with CRC enrolled into Arm 3 or Arm 4 are not eligible to be re-enrolled in the study on Arm 1 or Arm 2 following discontinuation.*

*Note – Subjects who have withdrawn from standard treatment due to unacceptable toxicity warranting discontinuation of that treatment and precluding retreatment with the same agent before progression of disease will also be eligible.*

f. **Cohort F** – Have a histologically or cytologically confirmed metastatic solid tumor for which no more than 2 prior lines of therapy were administered and there is no available therapy that may convey clinical benefit.

AND

Be a Chinese subject from mainland China.

*Note – Chinese subjects from mainland China are not eligible for Cohorts A through E or Cohort G.*

2. Have measurable disease by irRECIST 1.1 criteria.
3. Be  $\geq 18$  years of age on the day of signing informed consent.
4. Have a performance status of 0 or 1 on the Eastern Cooperative Oncology Group (ECOG) Performance Scale (Appendix 12.4).
5. Demonstrate adequate organ function as defined in [Table 2](#) (labs to be obtained within 7 days of initiation of treatment).

Table 2 Adequate Organ Function Laboratory Values

System	Laboratory Value
Hematological	

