19. Blood for correlative studies (RNA and DNA samples) and serum for exploratory protein analysis will be drawn prior to dosing on Day 1 of Cycle 1, on Day 1 of Cycle 2 (or Day 22 of Cycle 1 for subjects who do not receive a second dose of MK-4280 or MK-4280A), and at discontinuation. Detailed instructions for the collection and management of these samples are provided in the Procedure Manual.
20. This sample should be drawn for planned analysis of the association between genetic variants in DNA and drug response. If there is either a documented law or regulation prohibiting collection, or if the IRB/IEC does not approve the collection of the sample for these purposes, then this sample will not be collected at that site. If the sample is collected, leftover extracted DNA will be stored for FBR if the subject (or their legally acceptable representative) provides documented informed consent for FBR. If the planned genetic analysis is not approved, but FBR is approved and consent is given, this sample will be collected for the purpose of FBR.
21. Tumor tissue (archival or newly obtained biopsy) will be required at Screening for all subjects. For all subjects in Part B (except subjects in Cohort F), PD-L1 testing will be performed but does not need to be completed during Screening. For subjects in Part B (except subjects in Cohort F) with HNSCC (of oropharyngeal origin, only), prior HPV testing is required. For subjects with gastric cancer (except subjects in Cohort F), prior HER2/neu and EBV testing are required. For subjects with CRC and gastric cancer (except subjects in Cohort F), prior MSI testing is required. If subjects with HNSCC, gastric cancer, or CRC have not had these tests previously performed, they should be performed by the local laboratory at Screening. Leftover tissue may also be saved for Future Biomedical Research if the subject provides documented informed consent for FBR.
22. Post treatment tumor biopsy is optional, but strongly encouraged, for all subjects (except subjects in Cohort F) in Cycle 1 between Day 8 and Day 15. Leftover tissue may also be saved for FBR if the subject provides documented informed consent for FBR.
23. Pharmacodynamic receptor availability samples (predose) for all subjects (except subjects in Cohort F) will be drawn within 24 hours prior to start of infusion on Day 1 of Cycles 1-4, 6, 8, and every 4 cycles thereafter

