16. This sample should be drawn for planned analysis of the association between genetic variants in DNA and drug response. If there is either a documented law or regulation prohibiting collection, or if the IRB/IEC does not approve the collection of the sample for these purposes, then this sample will not be collected at that site. If the sample is collected, leftover extracted DNA will be stored for FBR if the subject (or legally acceptable representative) provides documented informed consent for FBR. If the planned genetic analysis is not approved, but FBR is approved and consent is given, this sample will be collected for the purpose of FBR.
17. Pharmacodynamic receptor availability samples (predose) for all subjects will be drawn within 24 hours prior to start of infusion on Day 1 of Cycles 1-4, 6, 8, and every 4 cycles thereafter
18. Postdose pharmacodynamic receptor availability samples will be drawn on Day 1 of Cycles 1, 2, 4, 6, and 8 at the end of the pembrolizumab infusion (+10 minutes), at the end of the MK-4280 infusion (+10 minutes), and 2 hrs after the start of the MK-4280 infusion ( $\pm$ 10 minutes). Additional postdose pharmacodynamic receptor availability samples in Cycles 1, 2, and 4 will be collected on Day 2 (Cycle 1 only), Day 8, and Day 15. Pharmacodynamic receptor availability samples will also be drawn at Discontinuation.
19. On Day 1 in Cycles 1-4, amylase and lipase samples should both be drawn predose and repeated 4 hours ( $\pm$ 10 mins) after the start of the first infusion. Beginning with Cycle 5, amylase and lipase should be drawn predose on Day 1 for all subjects.
20. Predose T-cell flow cytometry analysis samples will be drawn from subjects within 24 hours prior to start of infusion on Day 1 of Cycles 1-4. Postdose samples will be drawn on Day 8 of Cycle 1 only and on Day 15 of Cycles 1-4. The Sponsor may direct certain sites to not perform this assessment if it is determined to be infeasible for logistical or administrative reasons.
21. Tumor tissue (archival or newly obtained biopsy) will be required at Screening for all subjects. PD-L1 testing will be performed but does not need to be completed during Screening. Prior MSI testing is required. If subjects have not had these tests previously performed, they should be performed by the local laboratory at Screening. Leftover tissue may also be saved for Future Biomedical Research if the subject provides documented informed consent for FBR.

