23. Pharmacodynamic receptor availability samples (predose) will be drawn within 24 hours prior to start of infusion on Day 1 of Cycles 1-4, 6, 8, and every 4 cycles thereafter. Postdose pharmacodynamic receptor availability samples will be drawn on Day 1 of Cycle 1 at the end of the pembrolizumab infusion (+10 minutes), at the end of the MK-4280 infusion (+10 minutes), and 2 hrs after the start of the MK-4280 infusion ( $\pm$ 10 minutes). Additional postdose pharmacodynamic receptor availability samples in Cycle 1 will be collected on Day 2, Day 8, and Day 15. Pharmacodynamic receptor availability samples will also be drawn at Discontinuation.
24. On Day 1 in Cycles 1-4, amylase and lipase samples should both be drawn predose and repeated 4 hours ( $\pm$ 10 mins) after the start of the first infusion. Beginning with Cycle 5, amylase and

lipase should be drawn predose on Day 1.

25. Predose T-cell flow cytometry analysis samples will be drawn within 24 hours prior to start of infusion on Day 1 of Cycles 1-4. Postdose samples will be drawn on Day 8 of Cycle 1 only and on Day 15 of Cycles 1-4. The Sponsor may direct certain sites to not perform this assessment if it is determined to be infeasible for logistical or administrative reasons.
26. Tumor tissue (archival or newly obtained biopsy) will be required at Screening. PD-L1 testing will be performed but does not need to be completed during Screening. Prior MSI testing is also required. If subjects have not had these tests previously performed, they should be performed by the local laboratory at Screening.
27. Post treatment tumor biopsy is optional, but strongly encouraged, in Cycle 1 between Day 8 and Day 15.

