### **7.1.2.9 Tumor Tissue Collection and Biomarker Assessment**

Subjects will be requested to provide a tumor sample (archival or newly obtained pretreatment sample) as specified in the Procedure Manual. Sample collection, storage, and shipment instructions for correlative study samples, archival tumor samples, and newly obtained biopsy specimens will be provided in the Procedure Manual.

For all subjects in Part B, PD-L1 assessment will be performed but does not need to take place during the screening period.

For subjects in Part B with HNSCC (of oropharyngeal origin, only), HPV testing by p16 IHC, polymerase chain reaction (PCR), or fluorescent in situ hybridization is required before or during screening. For subjects in Part B with gastric cancer, HER2/neu testing via IHC and EBV testing via Epstein–Barr virus-encoded small RNAs (EBER1) in situ hybridization are required before or during screening. For subjects in Part B with gastric cancer or CRC, MSI testing by IHC or PCR is required before or during screening.

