##### **7.1.5.1 Screening**

Approximately 28 days prior to randomization, potential subjects will be evaluated to determine that they fulfill the entry requirements as set forth in Section 5.1.

Screening procedures may be repeated after consultation with the Sponsor.

Documented informed consent must be obtained prior to performing any protocol-specific procedure. Results of a test performed prior to the subject signing consent as part of routine clinical management are acceptable in lieu of a screening test if performed within the

specified time frame. Screening procedures are to be completed within 28 days prior to the first dose of trial treatment except for the following:

- Screening laboratory tests are to be performed within 7 days prior to the first dose of trial treatment.
- For women of reproductive potential, a urine pregnancy test will be performed within 72 hours prior to first dose of trial treatment. If urine pregnancy results cannot be confirmed as negative, a serum pregnancy test, performed by the local study site laboratory, will be required.
- For Arm 6 only: All women who are being considered for participation in Arm 6 of the study, and who are not surgically sterilized or postmenopausal, must be tested for pregnancy within 24 hours of the first dose of study intervention. If a urine test is positive or not evaluable, a serum test will be required.

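### Section 5.1.2 waives MSI/MMR testing when status is unknown, but 7.1.2.9 and three flow-chart footnotes require it by screening, and the MSS definition of CRC Cohorts A, B and G is not carried into eligibility

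*Combined protocol and SAP*

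**What the plan says.** Eligibility. The note after Cohort E in 5.1.2 excludes gastric cancer and CRC known to be MSI-high or MMR-deficient and defines both terms. It then says that if a subject's "MSI/MMR status is unknown, testing is not required to determine eligibility". Criteria 1a to 1c, which govern CRC Cohorts A, B and G, set out tumor site, stage and prior therapy. They do not mention MSS, and 5.1.3 adds no MSI criterion.

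Procedures. Section 7.1.2.9: "For subjects in Part B with gastric cancer or CRC, MSI testing by IHC or PCR is required before or during screening". Flow chart 6.1, footnote 21: "For subjects with CRC and gastric cancer (except subjects in Cohort F), prior MSI testing is required". Flow chart 6.2, footnote 21 (Arms 3 and 4): "Prior MSI testing is required. If subjects have not had these tests previously performed, they should be performed by the local laboratory at Screening". Flow chart 6.3, footnote 26 (Arm 6): "Prior MSI testing is also required".

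Timing. Section 7.1.5.1: "Screening procedures are to be completed within 28 days prior to the first dose of trial treatment except for the following"; MSI testing is not among the exceptions. The same section says that "potential subjects will be evaluated to determine that they fulfill the entry requirements as set forth in Section 5.1".

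Population and analysis. Section 2.1.2 describes Cohorts A, B and G as MSS CRC, and the objectives in Section 3 repeat this for B and G. The efficacy population in 8.5.3 is every treated subject with measurable disease on a baseline scan. Section 8.10 plans ORR by baseline PD-L1 status only. Section 4.2.3.6 lists candidate biomarkers "and microsatellite instability (MSI) will also be assessed by appropriate tests".

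**The concern.** The same test is optional for eligibility in one section and mandatory in four other places, and the optional wording sits in the section against which sites check entry. The cohort definition in 2.1.2 is not turned into an entry criterion, so a subject can be eligible without having been shown to belong to the population named.

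The consequence is greatest for the Cohort A combination arms (2A, 2C and 5). Section 4.2.1 gives the reason for choosing MSS CRC, namely that it scarcely responds to PD-1 monotherapy, and sets the result against an ORR of about 1-2% for approved third-line agents. There is no pembrolizumab-only arm to absorb a difference in case mix. Sections 4.2.1.1 and 4.2.1.3 already attribute the activity seen in this study to MSS CRC and use it to justify Arms 3, 4 and 6, so the label carries weight. Arm 6 is less exposed because 4.2.1.3 frames it against doublet combinations. For Cohort B, Arm 1 and Cohort E the matter is essentially the conflicting text.

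**Working it through.** The main check is a comparison of passages; the arithmetic only gives scale.

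1. **Can the passages all be followed?** If 7.1.2.9 and the footnotes are followed and the result is back before allocation, every CRC or gastric subject in Cohorts A to E and G has known status, an MSI-high result excludes the subject under the 5.1.2 note, and the waiver does no work in those cohorts. The waiver operates there only if the test was not done or the result is pending.

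2. **What routes remain?** Section 7.1.5.1 requires screening procedures to be complete before first dose, which closes most of the gap. Two routes are left: a site relies on the 5.1.2 note and does not test, or the sample is tested in screening but the result is outstanding at allocation. No passage requires the result to be available.

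3. **Is relief for MSI written elsewhere?** PD-L1 assessment is expressly allowed after screening (7.1.2.9), and BRAF testing is dropped where no local test exists (6.1, footnote 29). No comparable sentence covers MSI in Cohorts A to E or G. Footnote 21 of 6.1 exempts Cohort F; 7.1.2.9 does not repeat that exemption.

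4. **Does such a subject stay in the analysis?** Yes. The definition in 8.5.3 makes no reference to MSI status.

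5. **Weight of one non-MSS responder.**
   - Arms 2C and 5, Cohort A (N=40 each): 1/40 = 2.5 percentage points.
   - Arm 2A, Cohort A, maximum (N=100): 1/100 = 1 point.
   - Arm 2A expansion rule (2 of 10): 1 of the 2 responses needed.

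6. **Illustration for the expansion rule.** Let X ~ Bin(10, p + x), where p is the ORR in truly MSS subjects and x is the amount that non-MSS responders add to the per-subject ORR. Both are assumptions: p = 1-2% borrows the third-line benchmark in 4.2.1, which is not a rate for this combination, and x = 0.5, 1 or 2 points has no source in the documents. P(X ≥ 2) = 1 − (1−q)^10 − 10q(1−q)^9, with q = p + x.

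| x (points) | p = 1% | p = 2% |
|---|---|---|
| 0 | 0.43% | 1.62% |
| 0.5 | 0.93% | 2.46% |
| 1 | 1.62% | 3.45% |
| 2 | 3.45% | 5.82% |

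For example, p = 1% and x = 0 gives 1 − 0.99^10 − 0.10 × 0.99^9 = 1 − 0.9044 − 0.0914 ≈ 0.0043 (unrounded terms). Across the assumed range the probability of meeting the trigger stays below 6%.

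**The case against.** The best defense is that the passages answer different questions. Section 5.1.2 says testing is not needed to decide eligibility. Section 7.1.2.9 concerns tissue and biomarkers and lists MSI with HPV and EBV, which must also be tested by screening and are not entry criteria. A compulsory procedure and a separate eligibility rule can coexist. That reading is possible, but no passage states it, and it does not remove the problem: under it too, a subject not shown to be MSS can enter a cohort defined as MSS.

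Three further points stand. First, MSS is implemented in substance when the procedures are followed, because the test makes status known, the 5.1.2 note then excludes MSI-high and MMR-deficient tumors, and 7.1.1.2 has all criteria reviewed. Second, the waiver is not redundant: Cohort F is exempt from MSI testing under footnote 21 of 6.1 and may contain CRC or gastric cancer of unknown status, so deleting the sentence outright would be wrong. Third, the supplemental SAP is not available, and an ORR summary by MSI status may already be in it; silence in 8.10 does not prove a gap.

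A reader might infer that MSI-high subjects have been enrolled, or that the reported MSS CRC activity is contaminated. The documents do not support that. They show no case of either route, and the description of treated subjects as MSS in 4.2.1.3 fits with status having been ascertained, though it does not prove it. A reader might also infer that the Arm 2A expansion decision was compromised. The table shows a small effect under assumed inputs, 8.7 lets the sponsor expand below 2 of 10 after reviewing all data, and that interim may already be past.

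**Conclusion.** The inconsistency is real and lies in operative text. Section 5.1.2 waives a test that 7.1.2.9 and three footnotes require, and the MSS definition of Cohorts A, B and G is missing from the eligibility criteria. A subject of unknown status can meet 5.1.2 and count in an ORR described as MSS CRC.

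The exposure is limited. It is nil where 7.1.2.9 is followed with results back before allocation. Otherwise it cannot be computed, because the documents give neither the prevalence of MSI-high CRC nor its response rate. That the bias would be upward is an inference from the exclusion in 5.1.2 and from the low PD-1 responsiveness of MSS CRC stated in 4.2.1. One non-MSS responder is worth 2.5 points at N=40 or 1 point at N=100; the trigger probabilities are illustrative only. ORR is a secondary endpoint and 8.7 rules out hypothesis testing, so no formal decision is affected. The point should be fixed because the MSS label supports the reading of Cohort A and the case for later arms, and the remedy uses a test already mandated.

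**What to change.** - **Reconcile** the 5.1.2 note with 7.1.2.9, footnote 21 of 6.1, footnote 21 of 6.2, footnote 26 of 6.3, and 7.1.5.1.
- **Limit the waiver sentence to Cohort F**, and state the Cohort F exemption in 7.1.2.9 as well as in the 6.1 footnote.
- **Add to 5.1.2** that, for CRC Cohorts A, B and G, the MSI/MMR result already required in screening must be available before allocation and must not be MSI-high or MMR-deficient by the note's own definitions. Align the Cohort E wording.
- **Add to 8.6.2 or 8.10**, or confirm in the supplemental SAP, ORR in CRC subjects confirmed as not MSI-high and MMR-proficient, beside the full analysis set estimate, with the number untested or pending at allocation. The MSI data foreseen in 4.2.3.6 could supply this for subjects already enrolled.

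The cost is a few sentences of protocol text and one analysis line. No new procedure is needed. The downside is a possible short wait for a result within the 28-day screening window. If few subjects remain to be enrolled, the analysis line brings most of the benefit.

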### 5.1.3 Subject Exclusion Criteria

The subject must be excluded from participating in the trial if the subject:

1. Has had chemotherapy, radiation, or biological cancer therapy within 4 weeks prior to the first dose of study therapy, or who has not recovered to CTCAE Grade 0 or 1 from the AEs due to cancer therapeutics administered more than 4 weeks earlier (this includes subjects who received previous immunomodulatory therapy with residual immune-related adverse events [irAEs]). Subjects receiving ongoing replacement hormone therapy for endocrine irAEs will not be excluded from participation in this study.

Note: Subjects with Grade 2 neuropathy are excluded from Arm 3 of Part B but may be eligible for all other arms of Part B.

2. Is currently participating and receiving study therapy, or has participated in a study of an investigational agent and received study therapy, or used an investigational device within 4 weeks of the first dose of study treatment.
3. Has received previous treatment with another agent targeting the LAG-3 receptor.

4. Has received previous treatment with an immunomodulatory therapy (eg, anti-PD-1/PD-L1 or CTLA-4 agent) and was discontinued from that therapy due to a Grade 3 or higher irAE.
5. Is expected to require any other form of antineoplastic therapy while on study.
6. Has a diagnosis of immunodeficiency or is receiving chronic systemic steroid therapy in excess of replacement doses, or on any other form of immunosuppressive medication. Subjects (ie, with asthma) that require intermittent use of bronchodilators, inhaled steroids, or local steroid injections would not be excluded from the study.
7. Has a history of a previous, additional malignancy, unless potentially curative treatment has been completed, with no evidence of malignancy for 5 years.
  - a. Note: The time requirement for no evidence of disease for 5 years does not apply to the tumor for which a subject is enrolled in the study. The time requirement does not apply to subjects who underwent successful definitive resection of basal cell carcinoma of the skin, superficial bladder cancer or in situ cervical cancer, or other in situ cancers.
8. Has known active central nervous system (CNS) metastases and/or carcinomatous meningitis. Subjects with previously treated brain metastases may participate provided they are radiologically stable, ie, without evidence of progression for at least 4 weeks by repeat imaging (note that the repeat imaging should be performed during study screening), clinically stable and without requirement of steroid treatment for at least 14 days prior to first dose of trial treatment.
9. Has had a severe hypersensitivity reaction to treatment with another monoclonal antibody.
10. Has an active autoimmune disease or a documented history of autoimmune disease, except vitiligo or resolved childhood asthma/atopy. Replacement therapy (eg, thyroxine, insulin, or physiologic corticosteroid replacement therapy for adrenal or pituitary insufficiency, etc.) is not considered a form of systemic treatment.
11. Has an active infection requiring therapy.
12. Has a history of (non-infectious) pneumonitis that required steroids or has current pneumonitis.
13. Has had a prior stem cell or bone marrow transplant.
14. Has a known history of or screens positive for Human Immunodeficiency Virus (HIV) (HIV 1/2 antibodies), or an active chronic or acute Hepatitis B (eg, hepatitis B surface antigen [HBsAg] reactive) or Hepatitis C infection (eg, hepatitis C virus [HCV] RNA [qualitative] is detected).
15. Has a history or current evidence of any condition, therapy, or laboratory abnormality that might confound the results of the study, interfere with the subject's participation for the full duration of the study, or is not in the best interest of the subject to participate, in the opinion of the treating investigator.

16. Has known psychiatric or substance abuse disorders that would interfere with cooperation with the requirements of the trial.
17. Is a regular user as determined by investigator judgement (including “recreational use”) of any illicit drugs or has a recent history (within the last year) of substance abuse (including alcohol), at the time of signing informed consent.
18. Has symptomatic ascites or pleural effusion. A subject who is clinically stable following treatment for these conditions (including therapeutic thoraco- or paracentesis) is eligible.
19. Has clinically significant heart disease that affects normal activities.
20. Has had major surgery in the past 4 weeks.
21. Has received a live or live-attenuated vaccine within 30 days before the first dose of study intervention. Seasonal flu vaccines that do not contain live virus are permitted. Refer to Section 5.5.2 for information on COVID-19 vaccines.

Subjects being considered for enrollment into Arm 4 with CRC in Part B are also excluded if any of the following additional criteria (22 through 24) apply:

22. Has plans to use, or is using, any herbal medications/supplements or any medications or foods that are strong inhibitors or inducers of cytochrome P450 3A 4/5  $\leq 1$  week prior to the start of study treatment.
23. Has received previous treatment with irinotecan.
24. Has a known diagnosis of Gilbert’s Syndrome.

Subjects being considered for enrollment into Arm 6 in Part B are also excluded if any of the following additional criteria (25 through 36) apply:

25. Has received previous treatment with lenvatinib.  
Note: Prior therapy with other kinase inhibitors that target VEGF are not exclusionary.
26. Has had major surgery within 3 weeks prior to first dose of study interventions. Note: Adequate wound healing after major surgery must be assessed clinically, independent of time elapsed for eligibility.
27. Has preexisting  $\geq$ Grade 3 gastrointestinal or non-gastrointestinal fistula.
28. Has urine protein  $\geq 1$  g/24 hours.  
Note: Subjects with proteinuria  $>1+$  on urine dipstick testing/urinalysis will undergo 24-hour urine collection for quantitative assessment of proteinuria.
29. Has a left ventricular ejection fraction (LVEF) below the institutional (or local laboratory) normal range, as determined by multigated acquisition (MUGA) or echocardiogram (ECHO).

30. Has radiographic evidence of encasement or invasion of a major blood vessel, or of intratumoral cavitation.

NOTE: The degree of proximity to major blood vessels should be considered because of the potential risk of severe hemorrhage associated with tumor shrinkage/necrosis following lenvatinib therapy.
31. Prolongation of QTcF interval to >480 ms.
32. Has clinically significant cardiovascular disease within 12 months from first dose of study intervention, including New York Heart Association Class III or IV congestive heart failure, unstable angina, myocardial infarction, cerebral vascular accident, or cardiac arrhythmia associated with hemodynamic instability. Note: Medically controlled arrhythmia would be permitted.
33. Has present or progressive accumulation of pleural, ascitic, or pericardial fluid requiring drainage or diuretic drugs within 2 weeks prior to enrollment. The subject can receive diuretic drugs as needed per the treating physician, outside of the above mentioned conditions. Consult with the Sponsor if the subject has more than trivial/trace fluid accumulation.
34. Serious nonhealing wound, ulcer or bone fracture.
35. Has presence of gastrointestinal condition including malabsorption that might affect the absorption of lenvatinib.
36. Has clinically significant hemoptysis or tumor bleeding within 2 weeks prior to the first dose of study drug.

